1.0 OBJECTIVES

Primary Objectives

1. To determine the efficacy (response rate) of nivolumab in combination with ibrutinib in patients with relapsed/refractory or high-risk untreated CLL by
 - a. Cohort 1: determine the response rate (CR/CRi) by 2008 IWCLL criteria
 - b. Cohort 2: determine the conversion rate from PR to CR/CRi by 2008 IWCLL criteria
 - c. Cohort 3: determine the response rate (CR/CRi)

Secondary Objectives

1. To determine the safety of nivolumab in combination with ibrutinib in patients with relapsed, refractory or high-risk untreated CLL/Richter transformation (RT).
2. To determine the progression-free survival of patients with relapsed, refractory or high-risk untreated CLL/RT treated with nivolumab in combination with ibrutinib.
3. To determine the overall survival of patients with relapsed, refractory or high-risk untreated CLL/RT treated with nivolumab in combination with ibrutinib.

Exploratory Objectives

1. To study immunological and molecular changes in peripheral blood, lymph node, and bone marrow in response to nivolumab and ibrutinib therapy.

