2.5.2 Ibrutinib forms a specific bond with the cysteine-481 of BTK.⁴⁶ It leads to highly potent BTK inhibition with an IC₅₀ of 0.5nM.⁴⁷ Treatment of CLL cells with ibrutinib induced apoptosis in a dose- and time- dependent manner which was independent of baseline cytogenetics, *IGHV* mutational status or baseline BTK protein expression.⁴⁸ Ibrutinib also induced apoptosis in normal B cells, but this was significantly less than that seen in CLL cells, indicating that CLL cells are more sensitive to ibrutinib than normal B cells. Ibrutinib treatment of CLL cells inhibited downstream signaling pathways including ERK1/2 phosphorylation, CD40L induced AKT phosphorylation and CD40L induced NF- κ B DNA binding.⁴⁸ Ponader et al. evaluated the role of the tissue microenvironment of CLL cells and its effect on treatment with ibrutinib.⁴⁹ They reported that ibrutinib treatment significantly inhibited CLL cell migration and survival in a nurse-like cells (NLC) co-culture assay. In this model, ibrutinib treatment significantly decreased the levels of CCL3 and CCL4 and inhibited chemotaxis towards CXCL12 and CXCL13. In an adoptive transfer TCL1 mouse model, ibrutinib treatment delayed CLL progression.⁴⁹ Ibrutinib has impressive monotherapy activity in patients with relapsed CLL. Byrd et al. reported an ORR of 71% with ibrutinib in the relapsed setting.^{50,51} However, most of the responses with ibrutinib are partial responses. The 30-month PFS was reported as 68.4%, with median PFS of 28.1 months in patients with del(17p) (O'Brien et al. ASCO 2014). Ibrutinib is approved by the FDA for patients with CLL who received at least one prior therapy and in patients with del(17p). Ibrutinib is well tolerated with diarrhea being the most common adverse event (mostly grade 1-2).⁵²

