3.0 STUDY POPULATION

3.1 Inclusion Criteria

1. Patients will have a diagnosis of CLL or SLL, refractory to and/or relapsed after at least one prior standard therapy or untreated with del(17p) by FISH (high-risk cytogenetics) and have an indication for treatment by IWCLL 2008 criteria⁵³ (Cohort 1) OR have been on ibrutinib for at least 9 months with measurable persistent disease (ALC > 4K/uL, any lymph node > 1.5 cm by CT scan, or > 30% lymphocytes on bone marrow aspirate differential) (Cohort 2) OR Patients will have a diagnosis of RT, refractory to and/or relapsed after at least one prior standard therapy or untreated with del(17p) by FISH (high-risk cytogenetics) (Cohort 3)
2. Age 18 years or older
3. Eastern Cooperative Oncology Group (ECOG) Performance Status ≤2
4. Patients must have adequate renal and hepatic function
 - Total bilirubin ≤1.5 x upper limit of normal (ULN). For patients with Gilbert's disease, total bilirubin up to ≤3 x ULN is allowed provided normal direct bilirubin.
 - Serum creatinine ≤1.5 x ULN
 - ALT and AST ≤3 x ULN
5. Females of childbearing potential must have a negative serum or urine beta human chorionic gonadotrophin (β-hCG) pregnancy test result within 24 hours prior to the first dose of treatment and must agree to use an effective contraception method during the study and for 23 weeks following the last dose of the study drugs. Females of non- childbearing potential are those who are postmenopausal greater than 1 year or who have had a bilateral tubal ligation or hysterectomy. Males who have partners of childbearing potential must agree to use an effective contraceptive method during the study and for 31 weeks following the last dose of study drugs
6. Patients or their legally authorized representative must provide written informed consent.

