4.0 TREATMENT PLAN

4.1 Study Design

This is a phase II open label single-arm study to evaluate the combination of nivolumab and ibrutinib in patients with CLL.

COHORT 1 and 3	C1D1	C1D15	C2D1	C2D15	C3D1 and then Q2 weeks for a total of 96 weeks	After 96 weeks
Nivolumab*	3 mg/kg IV	3 mg/kg IV	3 mg/kg IV	3 mg/kg IV	3 mg/kg IV	—
Ibrutinib	—	—	Begin 420 mg orally once daily			
COHORT 2						
Nivolumab*	3 mg/kg IV	3 mg/kg IV	3 mg/kg IV	3 mg/kg IV	3 mg/kg IV	—
Ibrutinib	On ibrutinib stable oral daily dose for >9 months with residual CLL (PR) at enrollment, continue at same ibrutinib daily dose					

*** Note: After 3 cycles of treatment, the frequency of nivolumab administration may be decreased to once every 4 weeks, in consultation with the study PI.**

Each cycle is 28 days. Nivolumab dosing may be delayed for up to 3 days to accommodate for holidays/patient travel. Patients will receive nivolumab (3mg/kg IV over approximately 1 hour) monotherapy for the first cycle to assess for monotherapy toxicities of nivolumab. Nivolumab will continue for up to 24 cycles (96 weeks; 48 infusions). For Cohort 1 and cohort 3, ibrutinib will be initiated from the start of course 2. Treatment with ibrutinib will continue until disease progression, study termination, or a patient experiences a toxicity that requires discontinuation of ibrutinib. For Cohort 2, patients will have been on ibrutinib for >9 months, and ibrutinib dosing should continue. Nivolumab will be initiated after consent is provided, eligibility confirmed, and all pretreatment studies are complete. For patients with RT – ibrutinib may be introduced earlier than start of cycle 2, in case of worsening disease, after discussion with study PI.

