Additionally, patients who fulfill the criteria above for CR but who have the following will be considered a PR

- Patients with bone marrow nodules (may be noted as **nodular PR**). Immunohistochemistry should be performed to define whether these nodules are composed of primarily T cells or lymphocytes other than CLL cells, or CLL cells.
- Patients with persistent anemia or thrombocytopenia or neutropenia apparently unrelated to disease activity and more likely the consequence of persistent drug toxicity (may be noted as **CRI**).

Progressive Disease (PD): Characterized by ≥ 1 of the following events:

- Lymphadenopathy: $\geq 50\%$ increase in greatest determined diameter of any previous site; appearance of any new lesion, such as enlarged lymph nodes ($>1.5 \text{ cm}$), splenomegaly, hepatomegaly, or other organ infiltrates (NOTE: new lesion or isolated and/or transient increase in target lesion(s) in the setting of reduced lymph node size or organomegaly, or improvement in hemoglobin/platelets is not considered PD unless persists for >4 weeks (CT/PET scan confirmation required)
- $\geq 50\%$ increase in the previously noted enlargement of the liver or spleen; de novo appearance of hepatomegaly or splenomegaly

- $\geq 50\%$ increase in the absolute number of circulating lymphocytes to $\geq 5,000/\mu\text{L}$ (NOTE: In the absence of other objective evidence of PD, lymphocytosis alone is not considered progressive disease)
- Transformation to a more aggressive histology (i.e., Richter's syndrome)
- Occurrence of cytopenia (neutropenia, anemia, or thrombocytopenia) attributable to CLL (decrease in hemoglobin ≥ 2 gm/dL or to <100 g/L; or decrease $\geq 50\%$ in platelets or to $<100,000/\mu\text{L}$) that occurs ≥ 3 months after treatment, if the marrow biopsy demonstrates an infiltrate of clonal CLL cells.

Stable Disease (SD): Patients who do not fulfill the criteria for complete or partial response as defined above but do not exhibit progressive disease will be considered as having stable disease.

Responses for patients with RT will be assessed by non-Hodgkin's lymphoma (NHL) criteria.⁵⁵

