14.0 STATISTICAL CONSIDERATIONS

EFFICACY

A maximum of 72 patients will be enrolled in this Phase II study. Cohort 1 and 3 will enroll up to 24 patients each who were refractory to or relapsed after at least one prior standard therapy or untreated with del(17p) by FISH; Cohort 2 will enroll up to 24 patients who have been on ibrutinib for at least 9 months and have achieved a partial response.

Note: Statistical analysis and stopping rules, and toxicity assessment for Cohort 3 will be same as Cohort 1.

In the first cohort, the primary objective is to evaluate best response during the first 12-month of therapy. The primary efficacy endpoint, best response (BR), is defined as CR or CRi that occurs during the first 12 months of treatment. The optimum two-stage design proposed by Simon will be implemented.⁵⁶ We assume a target BR rate of 20% and a BR rate of 5% or lower will be considered not desirable. With a type I error rate of 10% and 80% power, we will enroll 9 patients in the first stage. If no patients achieve BR, the trial will be stopped. If 1 or more out of the first 9 patients have BR, accrual will continue until a total of 24 patients have been enrolled. We will suspend accrual at the end of the first stage, if all 9 patients have been enrolled, yet no responder (CR or CRi) has been observed. At the end of the study, if 3 or more out of the 24 patients achieve BR, the combination treatment will be considered efficacious and is worth further investigation. Under this Simon's two-stage design, the probability of early termination is 63% if the true BR is 5% and the expected sample size is 14.6 patients.

In the second cohort, the primary objective is to evaluate conversion rate during the first 12-month of therapy. The primary efficacy endpoint, conversion rate is defined as the conversion from partial response (PR) to complete response (CR/CRi) that occurs during the first 12 months of treatment. Up to 24 patients will be enrolled in this cohort. The same Simon's optimum two-stage design as described above will be used here in cohort 2. We assume a target conversion rate of 20% and a conversion rate of 5% or lower will be considered not desirable. With a type I error rate of 10% and 80% power, we will enroll 9 patients in the first stage. If no patient converts from PR to CR, the trial will be stopped. If 1 or more out of the first

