9 patients achieve conversion, accrual will continue until a total of 24 patients have been enrolled. We will suspend accrual at the end of the first stage, if all 9 patients have been enrolled, yet no conversion has been observed. At the end of the study, if 3 or more out of the 24 patients achieve conversion, the combination treatment will be considered efficacious and is worth further investigation. Under this design, the probability of early termination is 63% if the true conversion rate is 5% and the expected sample size is 14.6 patients.

TOXICITY

The Bayesian approach of Thall, Simon, Estey will be implemented for toxicity monitoring for patients enrolled in cohorts 1 and 2, where toxicity is defined as any grade 3 or higher non-hematological toxicity which is at least possibly related to the treatment.⁵⁷ The toxicity, denoted as TOX will be monitored by the Bayesian stopping boundaries calculated based on beta-binomial distributions. We assume as a priori, $p(\text{TOX}) \sim \text{beta}(0.6, 1.4)$. The study will be stopped for toxicity if $\text{Pr}(p(\text{TOX}) > 0.30 | \text{data}) > 0.8$. That is, we will stop the trial for new patient enrollment if at any time during the study we determine that there is more than 80% chance that the toxicity rate is more than 30%. The toxicity monitoring rule will be applied starting from the 6th patient, and then in cohort size of 6. The toxicity will be considered continuously throughout the study treatment duration. Stopping boundaries corresponding to this toxicity monitoring rule are shown in Table 14.1 below. The operating characteristics for toxicity monitoring are summarized in Table 14.2.

Table 14.1. Toxicity stopping boundaries in cohort size of 6 for patients enrolled in cohorts 1 and 2.

Number of patients	Stop the trial if there are this many patients having toxicity
6	3-6
12	6-12
18	8-18
24	10-24
30	12-30
36	14-36
42	16-42

Table 14.2. Operating characteristics for toxicity monitoring.

True Toxicity Rate	Early Stopping Probability	Average number of patients treated
0.1	0.02	47.3
0.2	0.12	43.4
0.3	0.41	33.8
0.4	0.81	20.7
0.5	0.98	11.7

ANALYSIS PLAN

Summary statistics will be provided for continuous variables. Frequency tables will be used to summarize categorical variables. The best response rate for cohort 1 and conversion rate for cohort 2 will be estimated along with the exact 95% confidence interval.

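### Cohort 2's inclusion criterion omits the partial response that sections 4.1 and 14 state and that the primary endpoint needs

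*Combined protocol and SAP*

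**What the plan says.** - **Section 3.1, item 1 (Cohort 2):** patients must "have been on ibrutinib for at least 9 months with measurable persistent disease". Persistent disease is shown by any one of three absolute findings: lymphocyte count above 4K/uL, a node above 1.5 cm on CT, or more than 30% lymphocytes in the marrow aspirate. No response category is mentioned.
- **Section 4.1, treatment table (Cohort 2):** "On ibrutinib stable oral daily dose for >9 months with residual CLL (PR) at enrollment".
- **Section 14.0, Efficacy:** Cohort 2 takes up to 24 patients "who have been on ibrutinib for at least 9 months and have achieved a partial response".
- **Section 1.0, objective 1b:** "determine the conversion rate from PR to CR/CRi by 2008 IWCLL criteria".
- **Section 14.0, endpoint:** "conversion rate is defined as the conversion from partial response (PR) to complete response (CR/CRi"), within the first 12 months of treatment. The cohort stops if none of the first 9 converts and succeeds "if 3 or more out of the 24 patients achieve conversion".
- **Section 10.0:** stable disease is a separate category: "Patients who do not fulfill the criteria for complete or partial response as defined above but do not exhibit progressive disease".

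**The concern.** The operative eligibility list is broader than the population for which the endpoint is defined. Its three thresholds are the CR thresholds of section 10.0 turned round (lymphocytes below 4000/uL, no node above 1.5 cm, under 30% marrow lymphocytes). They show that a patient is not in CR. They do not show PR, which section 10.0 defines by a reduction of at least 50% in a disease measure plus a blood-count condition, held for at least 2 months.

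A stable-disease patient with, say, a 2 cm node after 9 months of ibrutinib therefore satisfies criterion 1, and nothing in section 3.2 names response status as a reason to exclude. That patient cannot convert from PR, yet takes one of 24 places and possibly one of the 9 that decide whether the cohort continues. At stake is the chance of recognising a combination that does convert PR patients at the target rate.

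**Working it through.** **Inputs from section 14.0:** null rate 5%, target rate 20%, type I error 10%, power 80%, stop at 0 of 9, success at 3 or more of 24. **Assumed:** f, the share of Cohort 2 entrants not in PR.

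**Step 1. Reproduce the plan.** With conversion probability p, X ~ Bin(9, p) in stage 1 and Y ~ Bin(15, p) in stage 2:

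- P(stop) = (1 − p)^9
- P(success) = Σ (x = 1 to 9) P(X = x) · P(Y ≥ max(0, 3 − x))
- Expected N = 9 + 15 · (1 − P(stop))

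At p = 0.05: P(stop) = 0.95^9 = 0.630 (plan: 63%); expected N = 9 + 15 × 0.370 = 14.55 (plan: 14.6); P(success) = 0.093, within the 10% limit.

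At p = 0.20: P(stop) = 0.8^9 = 0.134; P(success) = 0.3020 × 0.8329 + 0.3020 × 0.9648 + 0.2618 = 0.805 (plan: 80%).

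The design arithmetic is sound, but power exceeds its target by only about 0.5 percentage points.

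**Step 2. Score a non-PR entrant.** The endpoint is conversion from PR and the rule counts conversions out of 24 patients. A patient who enters outside PR therefore contributes zero to the numerator and one to the denominator.

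**Step 3. Dilution.** The rate among all entrants becomes 0.20(1 − f) under the target and 0.05(1 − f) under the null. Putting these into the Step 1 formulas:

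| f (f × 24 patients) | Rate at target | Power | False stop at 0/9 | Rate at null | Type I error |
|---|---|---|---|---|---|
| 0 | 0.200 | 80.5% | 13.4% | 0.0500 | 9.3% |
| 5% (1.2) | 0.190 | 77.7% | 15.0% | 0.0475 | 8.3% |
| 10% (2.4) | 0.180 | 74.5% | 16.8% | 0.0450 | 7.3% |
| 25% (6) | 0.150 | 62.9% | 23.2% | 0.0375 | 4.7% |

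**Step 4. Whole-patient check.** Suppose one entrant among the first 9 and one among the next 15 are not in PR, leaving 8 and 14 patients who can convert. At 20%, P(stop) = 0.8^8 = 16.8% and power = 0.3355 × 0.8021 + 0.2936 × 0.9560 + 0.2031 = 75.3%. At 5%, type I error is 7.5%.

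**Step 5. Can the documents bound f?** The only related figure is in section 2.5.2, where a cited ibrutinib study "reported an ORR of 71% with ibrutinib in the relapsed setting", which leaves 100 − 71 = 29% without a response. That does not estimate f, because patients who have stayed on the drug for 9 months are selected for benefit.

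**The case against.** The strongest reply is that the protocol must be read as a whole. Sections 4.1 and 14.0 state PR in terms of who is enrolled, the objective and endpoint repeat it, and section 4.1 requires eligibility to be confirmed before nivolumab starts. The intended population is clear, and a stable-disease patient is eligible only if section 3.1 is read alone. Section 10.0's PR is also permissive (one disease reduction plus one blood-count condition), so few patients kept on ibrutinib for 9 months may fall outside it. All of this stands. It limits the likely size of f and makes this an omitted clause, not an error in the design. It does not remove the gap, because section 3.1 is the list against which patients are screened. Exclusion 20 does not close it either: it covers severe conditions or laboratory abnormalities at the investigator's discretion.

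A reader might go further and infer that type I error could exceed 10%, if a non-PR entrant's later CR/CRi were scored as a conversion. The documents do not support that. The endpoint starts from PR, so such scoring would misapply it. Even then, these patients would have to reach CR/CRi more often than 8.2%, 6.6% or 5.6% of the time (f = 5%, 10%, 25%), each above the 5% null rate assumed for patients already in PR. Nothing in the documents suggests this. Under the defined scoring, type I error falls.

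**Conclusion.** Wrong as written, as a minor inconsistency between the eligibility criterion and the primary endpoint. Criterion 1 admits patients who cannot meet the Cohort 2 endpoint, while sections 4.1 and 14.0 describe a population in PR. The consequence is conservative: some loss of power and some extra risk of a false futility stop.

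The size rests wholly on f. It also rests on non-PR patients entering at random across the two stages and being scored as the endpoint's wording implies. With little slack in the design, f = 5% already takes power below 80%, but only by 2.3 points (80 − 77.7). The 62.9% figure needs about 6 of 24 entrants outside PR, contrary to sections 4.1 and 14.0. If screening follows those sections in practice, the effect is close to nil.

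**What to change.** Reconcile section 3.1 with sections 4.1 and 14.0. Add to criterion 1 for Cohort 2 a requirement such as: *and in PR at enrollment by section 10.0, judged against values from before ibrutinib was started, where available*. The reference point is worth stating because section 10.0 measures lymphocyte change from a pretreatment baseline without saying which treatment is meant for patients already on ibrutinib. Leave the measurable-disease list, the 9/24 sample sizes and the decision rules as they are; none of the design figures changes.

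Optionally, section 14.0 could say outright that a Cohort 2 patient found not to be in PR at entry stays in the denominator as a non-converter. This only spells out what the endpoint and decision rule already imply.

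If the sponsor does want the broader population, objective 1b, the endpoint and the 5%/20% hypotheses need restating instead.

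The cost is one clause, a somewhat narrower Cohort 2 pool (the documents do not show by how much), and retrieval of pre-ibrutinib values from the chart. Those values, imaging in particular, may not exist for every candidate.

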3.2 Exclusion Criteria

1. History of another primary invasive malignancy that has not been definitively treated or in remission for at least 2 years. Patients with non-melanoma skin cancers or with carcinomas in situ are eligible regardless of the time from diagnosis (including concomitant diagnoses). If patients have another malignancy that was treated within the last 2 years, such patients may be enrolled if the likelihood of requiring systemic therapy for this other malignancy within 2 years is less than 10%, as determined by an expert in that particular malignancy at MD Anderson Cancer Center and after consultation with the Principal Investigator
2. Any major surgery, radiotherapy, cytotoxic chemotherapy, biologic therapy, immunotherapy, immunomodulatory drugs, experimental therapy within 4 weeks prior to the first dose of the study drugs. Note: Prior therapy with anti CD20 monoclonal antibody, anti CD52 monoclonal antibody, and lenalidomide are allowed. For oral targeted therapies (such as idelalisib, venetoclax), a washout of 3 days is allowed.
3. Significant cardiovascular disease such as uncontrolled or symptomatic arrhythmias, congestive heart failure, or myocardial infarction within 2 months of screening, or any Class 3 or 4 cardiac disease as defined by the New York Heart Association Functional Classification.
4. History of stroke or cerebral hemorrhage within 2 month.
5. Patients who have uncontrolled hypertension (defined as sustained systolic blood pressure \geq 160 mmHg or diastolic \geq 100 mmHg)
6. Known evidence of active cerebral/meningeal CLL. Patients may have history of CNS leukemic involvement if definitively treated with prior therapy and no evidence of active disease at the time of registration.
7. Active, uncontrolled autoimmune hemolytic anemia or immune thrombocytopenia requiring steroid therapy.
8. Patients with autoimmune diseases are excluded: Patients with a history of Inflammatory Bowel Disease (including Crohn's disease and ulcerative colitis) are excluded from this study as are patients with a history of autoimmune disease (e.g., rheumatoid arthritis, systemic progressive sclerosis, systemic lupus erythematosus, Wegener's granulomatosis).
9. Patients with previous allogeneic stem cell transplant (SCT) within 6 months or with active acute or chronic graft-versus host disease are excluded. Patients must be off immunosuppression for GVHD for at least 30 days before cycle 1 day 1.
10. Patients with organ allografts (such as renal transplant) are excluded.
11. History of interstitial lung disease or pneumonitis.
12. Patients who are on high dose steroids (>10 mg daily of prednisone or equivalent) or immune suppression medications. Note: Patients on high-dose steroids (doses >10 mg/day of prednisone or equivalent) or immune suppression medications are eligible provided these drugs are discontinued at least 3 days prior to starting on the study drugs.
13. Patients with uncontrolled active infection (viral, bacterial, and fungal) are not eligible.
14. Current or chronic hepatitis B or C infection, or known seropositivity for HIV.
15. Patient is pregnant or breast-feeding.
16. Concurrent use of investigational therapeutic agent.
17. Malabsorption syndrome or other condition that precludes enteral route of administration.

18. Concomitant use of warfarin or other Vitamin K antagonists.
19. Requires treatment with a strong cytochrome P450 (CYP) 3A inhibitor (see Appendix 2).
20. Other severe acute or chronic medical or psychiatric condition or laboratory abnormality that in the opinion of the investigator may increase the risk associated with study participation or investigational product administration or may interfere with the interpretation of study results and/or would make the patient inappropriate for enrollment into this study.

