6.2 Dose modifications for ibrutinib

Interrupt ibrutinib for any Grade 3 or greater non-hematological, Grade 3 or greater neutropenia with infection or fever, or Grade 4 hematological toxicities. Once the symptoms of the toxicity have resolved to Grade 1 or baseline, reinitiate ibrutinib at the starting dose. If the toxicity reoccurs, reduce dose by one capsule (140 mg per day).

NOTE: As diarrhea could occur from the use of ibrutinib or nivolumab, patients with grade 2 diarrhea should have their ibrutinib held.

Recommended dose modifications are described below:

Toxicity Occurrence	Dose modification Starting Dose = 420 mg daily
First	Restart at 420 mg daily
Second	Restart at 280 mg daily
Third	Restart at 140 mg daily
Fourth	Discontinue ibrutinib

Dose Modifications for Use with CYP3A Inhibitors/Inducers: Ibrutinib is metabolized primarily by CYP3A. Concomitant use of strong CYP3A inhibitors which would be taken chronically (e.g., ritonavir, indinavir, nelfinavir, saquinavir, boceprevir, telaprevir, nefazodone) is not recommended. For strong CYP3A inhibitors used short-term (e.g., antifungals and antibiotics for 7 days or less, e.g., ketoconazole, itraconazole, voriconazole, posaconazole, clarithromycin, telithromycin), consider holding ibrutinib therapy during the duration of the inhibitor use. Avoid strong CYP3A inhibitors that are needed chronically. If a moderate CYP3A inhibitor must be used (e.g., fluconazole, darunavir, erythromycin, diltiazem, atazanavir, aprepitant, amprenavir, fosamprevir, verapamil, grapefruit products and ciprofloxacin), reduce ibrutinib dose to 140 mg daily.

Avoid grapefruit and Seville oranges during ibrutinib treatment, as these contain moderate inhibitors of CYP3A. Avoid Star fruit as it contains inhibitors of CYP3A.

Administration of ibrutinib with strong inducers of CYP3A can decrease ibrutinib plasma concentrations. Concomitant use of strong CYP3A inducers (e.g., rifampin, rifabutin, phenytoin, carbamazepine, and St. John's Wort) are not recommended.

A list of common CYP3A inhibitors and inducers is provided in Appendix 2; a comprehensive list of inhibitors, inducers, and substrates may be found at

<http://medicine.iupui.edu/clinpharm/ddis/table.aspx>. This website is continually revised and should be checked frequently for updates.

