7.2 Excluded concomitant therapy

Use of the following therapies is prohibited during the study:

- Cytotoxic chemotherapy
- Immunotherapy (outside of this study)
- Radiotherapy (Note: Localized radiotherapy to an area not compromising bone marrow function is allowed)
- Any therapies intended for the treatment of lymphoma/leukemia whether FDA-approved or experimental (outside of this study)
- Steroid therapy for anti-neoplastic intent. Inhaled steroids for asthma, topical steroids, steroids as part of premedication for nivolumab, or replacement/stress corticosteroids are permitted.
- Strong CYP3A inhibitors which would be taken chronically
- Grapefruit, Seville oranges, Star fruit
- Strong CYP3A inducers (e.g., rifampin, rifabutin, phenytoin, carbamazepine, and St. John's Wort) are not recommended

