Appendix 2: Inhibitors and Inducers of CYP3A4/5

Inhibitors of CYP3A4/5 are defined as follows. A comprehensive list of inhibitors can be found at the following website: <http://medicine.iupui.edu/clinpharm/ddis/table.aspx>. The general categorization into strong, moderate, and weak inhibitors according to the website is displayed below. Refer to Section 6.2 on instructions for concomitant use of CYP3A4/5 inhibitors or inducers with ibrutinib.

Inhibitors of CYP3A4/5	Inducers of CYP3A4/5
Strong inhibitors: INDINAVIR NELFINAVIR RITONAVIR CLARITHROMYCIN ITRACONAZOLE KETOCONAZOLE NEFAZODONE SAQUINAVIR SUBOXONE TELITHROMYCIN	Carbamazepine Efavirenz Nevirapine Barbiturates Glucocorticoids Modafinil Oxcarbazepine Phenobarbital Phenytoin Pioglitazone Rifabutin Rifampin St. John's Wort Troglitazone
Moderate inhibitors: aprepitant erythromycin diltiazem fluconazole grapefruit juice Seville orange juice verapamil	
Weak inhibitors: cimetidine	
All other inhibitors: amiodarone NOT azithromycin chloramphenicol boceprevir ciprofloxacin delavirdine	
fluvoxamine gestodene mibepradil mifepristone norfloxacin norfluoxetine star fruit telaprevir voriconazole	

Source: <http://medicine.iupui.edu/clinpharm/ddis/table.aspx>

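### Exclusion 19 cites only Appendix 2 for strong CYP3A inhibitors, but four drugs that Section 6.2 names as strong are missing from that table's strong group

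*Combined protocol and SAP*

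**What the plan says.** Exclusion 19 (Section 3.2) reads "Requires treatment with a strong cytochrome P450 (CYP) 3A inhibitor (see Appendix 2". It says nothing about how long the inhibitor is taken, and Appendix 2 is its only pointer.

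Appendix 2 opens with "Inhibitors of CYP3A4/5 are defined as follows" and sorts inhibitors into strong, moderate, weak and all other. Its strong group is "INDINAVIR NELFINAVIR RITONAVIR CLARITHROMYCIN ITRACONAZOLE KETOCONAZOLE NEFAZODONE SAQUINAVIR SUBOXONE TELITHROMYCIN". It sends the reader to Section 6.2 for how to handle concomitant use, and to an outside website for a comprehensive list.

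Section 6.2 describes the same table more loosely: "A list of common CYP3A inhibitors and inducers is provided in Appendix 2". It then names strong inhibitors itself, in two sets. One is a set of examples for chronic use that includes boceprevir and telaprevir, with the instruction "Avoid strong CYP3A inhibitors that are needed chronically". The other is "For strong CYP3A inhibitors used short-term (e.g., antifungals and antibiotics for 7 days or less, e.g., ketoconazole, itraconazole, voriconazole, posaconazole, clarithromycin, telithromycin", for which the advice is to consider holding ibrutinib while the inhibitor is taken.

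Section 7.2 prohibits on study "Strong CYP3A inhibitors which would be taken chronically". It names no drugs under that entry.

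**The concern.** An eligibility rule should give the same answer whoever applies it. Here the rule turns on the word strong, and the one list it cites does not match the list in the section that governs ibrutinib dosing. A screener who works from the table could judge that a patient on voriconazole or posaconazole passes exclusion 19. A screener who also reads Section 6.2 would judge that the patient fails it.

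The criterion has a real purpose. Section 5.2.3 states that ibrutinib is eliminated mainly by metabolism, chiefly through CYP3A. Section 6.2 gives a reduced ibrutinib dose for use with a moderate inhibitor but none for use with a strong one. A patient enrolled on a long-term strong inhibitor would therefore have to stop it, switch to another drug, or go without ibrutinib.

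**Working it through.** The plan states no figure on this point, so the check is a comparison of the two lists.

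**Strong in Section 6.2**
- Chronic examples: ritonavir, indinavir, nelfinavir, saquinavir, nefazodone, boceprevir, telaprevir = 7.
- Short-term examples: ketoconazole, itraconazole, clarithromycin, telithromycin, voriconazole, posaconazole = 6.
- Total: 7 + 6 = 13.

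**Strong in Appendix 2**
- 10 entries, of which 9 are also in the Section 6.2 set.

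**Differences**
- Strong in Section 6.2 but not in the strong group of Appendix 2: 13 − 9 = 4.
- Strong in Appendix 2 only: 10 − 9 = 1 (Suboxone).

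| Drug | Section 6.2 | Appendix 2 |
|---|---|---|
| Voriconazole | Strong (short-term example) | All other inhibitors |
| Posaconazole | Strong (short-term example) | Not listed |
| Boceprevir | Strong (chronic example) | All other inhibitors |
| Telaprevir | Strong (chronic example) | All other inhibitors |
| Suboxone | Not mentioned | Strong |

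The extracted Appendix 2 table is split in two, so I checked whether the split could explain the mismatch. The second block carries on the all-other group in near-alphabetical order and ends with voriconazole. The strong group is separate and in capitals. A page break does not account for the difference.

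**Which patients could be enrolled in error**
- *Boceprevir or telaprevir.* Sections 5.2 and 6.2 both name these as strong. If they are given for hepatitis B or C or HIV, exclusion 14 already applies. The documents do not state their use, so this is an assumption.
- *Voriconazole or posaconazole, 7 days or less.* Section 6.2 accommodates this with a possible ibrutinib hold. Enrolment does not lead to a prohibited combination.
- *Voriconazole or posaconazole, long term.* Exclusion 13 removes patients whose active infection is uncontrolled, but not those taking an azole for a controlled infection or as prophylaxis. Section 5.2 does not name the azoles. Once Section 6.2 is read for their strength, Section 7.2 prohibits chronic use. This is the case that remains open.

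**When the problem would surface.** Section 8.0 has concurrent medications recorded within 14 days of the first dose, so the drug would be on file, but the screener still has to classify it. In Cohorts 1 and 3 ibrutinib normally starts at cycle 2, after a 28-day cycle, although Section 4.1 lets it start sooner in Richter transformation. Cohort 2 patients enter already taking it.

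**The case against.** The strongest reply is that this is mostly editorial. All other inhibitors is not a strength class, so the table never says that voriconazole is less than strong. Section 6.2 presents Appendix 2 as a list of common inhibitors, both places point to a website for the full list, and Appendix 2 sends the reader to Section 6.2, where all four drugs are named as strong. An error needs a screener who stops at the table and reads an ungraded entry as not strong. Section 5.2, Section 7.2, exclusions 13, 14 and 20, and medication recording stand behind that screener.

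Much of this stands, and it limits the size of the point. It does not remove it. The description as a common list explains why posaconazole is missing, but not why three drugs that are listed sit outside the strong group. Appendix 2 refers back to Section 6.2 for instructions on use, not for classification. Exclusion 19 does not cite the website, which Section 6.2 says is continually revised.

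A reader might infer more than the documents support:
- *That Appendix 2 classes all four drugs as not strong.* It gives three of them no strength and is silent on posaconazole.
- *That Section 6.2 bars voriconazole and posaconazole outright.* It names them only as short-term examples. It calls chronic strong inhibitors not recommended and says to avoid them. The prohibition is in Section 7.2 and covers chronic use only.
- *That Cohort 2 is put at new risk because ibrutinib is already running.* Those patients have been on it for more than 9 months. An inhibitor taken alongside it before enrolment would be an existing combination that screening failed to correct, not one that the trial created.

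**Conclusion.** The mismatch is real and worth correcting, as a matter of eligibility and safety wording. Of the 13 drugs that Section 6.2 names as strong, 4 are missing from the strong group of the only list that exclusion 19 cites: 3 are under an ungraded heading and 1 is absent. The practical exposure is narrower, namely a patient on long-term voriconazole or posaconazole who is not caught by another exclusion and whose screener uses the table alone.

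The documents do not say how many such patients to expect. I assume few. The conclusion also takes Section 6.2 as the intended classification. That is reasonable because Section 6.2 governs dosing, but the sponsor should confirm it, since Appendix 2 attributes its classes to an outside website that cannot be checked here. No endpoint, sample size, stopping boundary or analysis depends on this.

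**What to change.** 1. In Appendix 2, move voriconazole, boceprevir and telaprevir to the strong group and add posaconazole to it.
2. Have exclusion 19 cite Section 6.2 as well as Appendix 2, and limit it to chronic use, in line with Sections 6.2 and 7.2. Courses of 7 days or less would follow the ibrutinib hold guidance in Section 6.2. Without this limit, step 1 alone could exclude patients on a short azole course that Section 6.2 already accommodates. The amendment should also say how a finite course longer than 7 days is treated, which Section 6.2 leaves open.
3. Give Suboxone the same status in Section 6.2 and Appendix 2.

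The cost is an amendment to one table, one criterion and one entry in Section 6.2 or Appendix 2. The downside is that a few patients on long-term azoles would have to switch drug or be ineligible.

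Optional tidying: the moderate lists also differ. Ciprofloxacin is moderate in Section 6.2 but under All other inhibitors in Appendix 2, and darunavir, atazanavir, amprenavir and fosamprevir (as spelled in Section 6.2) are not in the table. This does not affect exclusion 19.
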